Exclusion Criteria	
• Infants born earlier than 37 weeks of gestation• Infants who are exclusively-formula fed or less than half of oral intake is from breastfeeding or from expressed breast milk at the time of enrollment• Infants born with medical complications (i.e., neurological, cerebral palsy, confirmed food allergies)• Diagnosis of other severe or complicating medical problems, including autoimmune or chronic immune inflammatory conditions, gastrointestinal inflammatory conditions, or renal insufficiency• History of abdominal surgery or congenital abnormalities of the GI tract, the cardiovascular system, the pulmonary system or the renal system• Antibiotic use (oral or systemic) within 7 days prior to enrollment• Parents' intent to feed non-study probiotics or solid food to their infant at any time during the study• Infants who have consumed any B. infantis-containing probiotics since birth• Primary Immune Deficiency• Maternal use of probiotics containing B. infantis after the baby's birth and/or intent to use probiotics containing B. infantis at any time throughout the study• Past or current medical problems or findings from physical examination or laboratory testing that are not listed above, which, in the opinion of the investigator, may pose additional risks from participation in the study, may interfere with the participant's ability
---------------------------	---

	to comply with study requirements or that may impact the quality or interpretation of the data obtained from the study
Study Procedures	Physical examination, stool collection, questionnaire administration
Statistical Considerations	20 FPIAP infants in each group, B. infantis INF108F versus placebo. Approximately 100 infants will be recruited and screened for the study to obtain a sample size of 50 participants for randomization, assuming a 50 percent screen fail rate. Forty (40) participants are expected to complete the study assuming a 20 percent drop-out rate. This sample size is based on a literature review of randomized clinical trials and the anticipated changes to the microbiome based on previous studies of B. infantis . Analysis on primary and secondary objectives will be completed based on the mITT population and the PP population; analysis on the exploratory objectives will be completed based on the mITT population.

Contents

SYNOPSIS	3
Glossary of Abbreviations/Definitions	10

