1. BACKGROUND AND SIGNIFICANCE

1.1 Background

Oral tolerance is one of the fundamental mechanisms in preventing food allergies in humans. Breaching of oral tolerance may potentially lead to the development of food allergies (FA). Allergic food reactions can be divided into 2 categories: immunoglobulin E (IgE)-mediated and non-IgE-mediated FA. The hallmark of IgE-mediated FA is the potential of life-threatening anaphylaxis. The frequency of IgE-mediated FA in US children is about 6-8%.

The non-IgE-mediated GI FA includes several clinical conditions, food protein-induced allergic proctocolitis (FPIAP), food protein induced enterocolitis syndrome (FPIES), eosinophilic esophagitis (EoE) and eosinophilic gastrointestinal disorder (EGID). FPIAP is likely the earliest manifestation of non-IgE-mediated FA in childhood, and perhaps the very first condition of breaching oral tolerance, as it occurs in early infancy (2 weeks to 2 months) (1). In a prospective birth cohort study (GMAP), we have demonstrated that a prevalence of 17% of infants with FPIAP typically present with mucusy bloody stools, GER, irritability and feeding intolerances (1), and have increased risk of developing IgE-mediated FA later in life (2). FPIAP is also a risk factor for developing EoE (3). Children with FPIAP often have eczema (1). These suggest a possible common mechanism in non-IgE-mediated and IgE-mediated conditions.

The human intestinal microbiome is found to play a key role in health and disease. Changes to the gut microbiota have been associated with a wide variety of diseases, including allergic diseases in human (4-9). It is known that the human gut microbiota undergoes rapid and dynamic changes during the first year of life (10-13). Many factors are known to influence the initial acquisition and subsequent composition of the gut microbiome in infants (11). These factors include mode of delivery, antibiotic exposure, presence of mother's milk and breastfeeding, social economic status and household living conditions (11). Additionally, prenatal factors and in-utero exposures to certain environments likely play a role in the acquisition and composition of the infant gut microbiota (11).

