3.1 Study Endpoints

3.1.1. Primary Endpoint

Changes to the gut microbiome composition (including *B. infantis* colonization) in infants with FPIAP over a 4-week period (*B. infantis* INF108F vs placebo)

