5.4. Randomization and Study Supply Shipment

Randomization lists will be maintained in a secured area by the study team. If the randomization key is shared such that blinding is compromised, the Principal Investigator will be notified.

Randomization will occur immediately after all screening and baseline tasks have been confirmed to be completed and baseline data has been deemed acceptable. Baseline tasks include:

- Confirming infant/mother eligibility
- Obtaining informed consent
- Confirming baseline data collection
- Confirming baseline stool specimen collection.

Only infants for whom acceptable baseline data and stool samples have been collected will be randomized into the supplementation phase of the study. Using the randomization key generated by an unblinded statistician and held by an unblinded study site team member, eligible infants will be assigned a randomization code and randomized to a study product arm. The unblinded team member will provide the enrolled patient's parents with

the appropriate Study Product Kit in accordance with the randomization key. Infants will be randomized in a 1:1 ratio to the following arms:

- 8.0×10^9 CFU *B. infantis* INF108F
- Lactose placebo

After randomization, the study team will provide the assigned feeding kit to the participant. Study supplies that will be provided include:

- Feeding kits to include 14 sachets of study product (*B. infantis* INF108F or lactose placebo depending on randomization), oral syringes, and mixing cups
- Stool collection kits

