9.2.2 Study Participant Populations

Randomization Approximately fifty (50) infants will be randomized in a 1:1 ratio to treatment probiotic or placebo. Randomization will occur immediately after all baseline period tasks have been confirmed to be completed and provide acceptable data.

Populations for Analyses The modified Intent to Treat (mITT) population will include all infants who are randomized and receive at least one supplementation. The Per Protocol (PP) population will include all randomized participants who do not have major protocol deviations. Major protocol deviations will be defined prior to unblinding of the data. Analysis on primary and secondary objectives will be completed based on the mITT population and the PP population; analysis on the exploratory objectives (perception of treatment) will be completed based on the mITT population.

Descriptive Statistics Descriptive statistics (mean, median, and standard deviation, minimum and maximum) of the quantitative variables will be summarized using number of subjects (n). The qualitative variables will be summarized using counts and percentages. All summaries will be presented by treatment group and time point (where relevant).

All CRF and laboratory data will be analyzed. Comparisons between treatment groups will be performed using Fisher's exact test or Pearson's Chi-Square test for categorical data and one-way ANOVA with Tukey's post hoc comparisons for individual timepoints or two-way repeated measures ANOVA for all timepoints for continuous data. Mean and standard deviations for certain groups and timepoints will be used as estimates in power calculations for future studies. Missing data will not be imputed in this study.

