9.2.3 Efficacy Analysis

Primary Endpoint(s) The primary objective of the study is to assess the effectiveness of the probiotic, *B. infantis* INF108F, on modulating the gut microbiome composition of breastfed infants diagnosed with FPIAP from Baseline to Day 28, including colonization of INF108F. This will be measured using stool 16S analysis and quantitative PCR. Treatments will be compared using a Wilcoxon Rank Sum test.

Secondary Endpoint(s) The secondary objectives of this study as measured:

- Evaluating the reduction in stool frequency and improvement of stool consistency by Day 7 using Questionnaire
- Evaluating the improvement of infant GER symptoms by Day 14 using Questionnaire. Reduction by 50 percent from Baseline to Day 14 Infants with a reduction in the number of crying/fussing episodes of greater than or equal to 50 percent on Day 14 will be counted as a success. The number of successes per treatment group will be compared using a Chi-square or Fisher's Exact test, as appropriate.
- Evaluating the improvement of feeding difficulties by Day 14, using Questionnaire. The number of successes per treatment group will be compared using a Chi-square or Fisher's Exact test, as appropriate.

- Evaluating the improvement of infant's sleep by Day 14, using Questionnaire.
- Changes of stool cytokine profile by Day 28. The changes from baseline to Day 28 will be compared for the two groups using a repeated measures ANOVA.

Safety Analysis Fisher's Exact Test will also be used to compare treatment groups for SAEs and AEs resulting in withholding or discontinuing the study products. Adverse events will be summarized. Frequencies and percentages of subjects with treatment-emergent adverse events (TEAEs), serious TEAEs and TEAEs causing premature discontinuation will be provided by treatment group. An AE is treatment emergent if it 1) occurs after the first dose of randomized study treatment or 2) if it is present prior to receipt of randomized study treatment but worsens in severity or increases in frequency after the first dose of randomized study treatment.

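### The primary Wilcoxon test in Section 9.2.3 does not say what it ranks and uses no baseline covariate, so power may be lost although a baseline stool is required before randomization

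*Combined protocol and SAP*

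**What the plan says.** Section 3.1.1 defines the primary endpoint as "Changes to the gut microbiome composition (including *B. infantis* colonization) in infants with FPIAP over a 4-week period", active against placebo. Section 9.2.3 restates it as an effect on composition in infants "diagnosed with FPIAP from Baseline to Day 28, including colonization of INF108F". On measurement it says "This will be measured using stool 16S analysis and quantitative PCR", and on analysis only "Treatments will be compared using a Wilcoxon Rank Sum test".

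No scalar variable is named, and the ranked quantity is not defined. Neither Section 9.2.3 nor the general methods in Section 9.2.2 (Fisher or chi-square tests, one-way and repeated measures ANOVA) include a baseline covariate for this endpoint. No stratification factor is stated.

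The baseline measurement should nevertheless exist. Section 5.4 says "Only infants for whom acceptable baseline data and stool samples have been collected will be randomized into the supplementation phase of the study", and Section 6.1.3 does not allow the first feeding until the baseline stool has been collected and frozen.

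**The concern.** A two-sample rank-sum test takes no covariate. The baseline value can therefore enter only by subtraction (a change score) or not at all (Day 28 alone). Subtraction fixes the baseline slope at 1, which adds noise if the true slope is lower. Ignoring baseline discards whatever it predicts about Day 28.

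The plan gives some reason to expect a modest correlation. Section 1.1 says "It is known that the human gut microbiota undergoes rapid and dynamic changes during the first year of life", and Section 1.4 describes a change in composition within days of starting the product. With about 20 completers per arm, precision is scarce, and a covariate that is collected anyway could be used at little cost.

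**Working it through.** **The plan's own figures.** The Synopsis states "20 FPIAP infants in each group". Section 9.1.1 reproduces: 100 screened × (1 − 0.50) = 50 randomized, and 50 × (1 − 0.20) = 40 completers, or 20 per arm. No alpha, power, effect size, SD or correlation is stated, so the loss cannot be computed from the documents alone.

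**Assumptions.** Two-sided 0.05; 20 per arm; a true shift of 0.8 Day 28 SDs; bivariate normal values; correlation ρ varied; k = baseline SD / Day 28 SD, taken as 1 or 0.5.

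**Variances, with Day 28 variance set to 1.**
- Day 28 alone: 1
- Change score: 1 + k² − 2ρk
- Baseline-adjusted (linear): 1 − ρ²
- Change minus adjusted: (k − ρ)², never negative. Day 28 minus adjusted: ρ², never negative.

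At k = 1, change against adjusted:
- ρ = 0.3: 1.40 vs 0.91 (35% less)
- ρ = 0.5: 1.00 vs 0.75 (25% less)
- ρ = 0.7: 0.60 vs 0.51 (15% less)

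At k = 0.5:
- ρ = 0.3: 0.95 vs 0.91 (4% less)
- ρ = 0.5: 0.75 vs 0.75 (no difference)
- ρ = 0.7: 0.55 vs 0.51 (7% less)

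The gain over a change score thus shrinks towards zero as k approaches ρ.

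**Simulated power (%), 20,000 replicates per row.** The adjusted test is Quade's rank ANCOVA: rank both values over all infants, regress Day 28 ranks on baseline ranks, and compare residuals between arms. Gains are in points, from unrounded values.

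| k | ρ | Wilcoxon, change | Wilcoxon, Day 28 | Rank ANCOVA | Gain over change | Gain over Day 28 |
|---|---|---|---|---|---|---|
| 1 | 0 | 39.5 | 66.6 | 65.9 | 26.4 | −0.7 |
| 1 | 0.3 | 52.9 | 66.9 | 69.9 | 17.0 | 3.0 |
| 1 | 0.5 | 66.9 | 66.8 | 77.0 | 10.1 | 10.2 |
| 1 | 0.7 | 87.4 | 66.8 | 89.2 | 1.9 | 22.5 |
| 1 | 0.8 | 96.9 | 67.4 | 96.1 | −0.8 | 28.7 |
| 0.5 | 0.3 | 69.5 | 67.0 | 70.1 | 0.6 | 3.1 |
| 0.5 | 0.5 | 78.3 | 66.5 | 76.3 | −2.0 | 9.7 |
| 0.5 | 0.7 | 89.7 | 66.9 | 89.1 | −0.6 | 22.2 |

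With no true effect, all three tests rejected in about 5% of replicates.

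**Effect size.** At a 1.0 SD shift and k = 1, power for the change score against rank ANCOVA is about 72 vs 87% (ρ = 0.3), 85 vs 91% (0.5) and 97 vs 98% (0.7). At 1.5 SD all three tests are at or above about 97%, so nothing practical is at stake.

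**Colonization.** Section 3 says *B. infantis* is absent from most infants in industrialized countries, and Section 4.2 excludes infants already given it. A separate simulation (4,000 runs) assumed that no infant carried it at baseline and that 10% vs 60% carried it at Day 28. Power was 94.0 / 94.0 / 94.5% for change, Day 28 and rank ANCOVA: no material difference. If 10% already carried it at baseline and kept it, the figures were 80 / 85 / 90%. The nil result therefore rests on baseline carriage being close to zero.

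**The case against.** The strongest reply is that this is an efficiency preference. The Wilcoxon test is valid under randomization, and the plan's authors may expect an effect large enough that any test would find it. That stands: no effect size is stated, so low power has not been shown. It also stands that the equal-SD assumption drives the gain over a change score, and that the gain is about nil for colonization, a named part of the endpoint, if baseline carriage is close to zero.

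A reader might infer that the plan ranks the change score and so surely loses power. The documents do not support this. Section 9.2.3 gives a period and a test, not the ranked variable. If change is ranked, baseline is already used by subtraction, and at a high correlation, or with k near ρ, little or nothing is lost. If Day 28 is ranked, the loss is small at low correlation and large at high correlation.

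A reader might also infer that chance baseline imbalance biases the primary result. Imbalance can move the estimate in a particular sample, but it does not bias the randomized comparison or inflate its type I error.

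Finally, Section 5.4 requires an acceptable stool sample, not a successful assay, so a few baseline values could still be missing.

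**Conclusion.** The point holds as a possible loss of efficiency. The primary test has no baseline covariate, the ranked quantity is undefined, and the baseline sample is collected anyway.

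Under the stated assumptions with equal SDs, adjustment gains about 2 to 17 points over a change score (ρ from 0.7 down to 0.3) and about 3 to 23 points over Day 28 alone (ρ from 0.3 up to 0.7). It gains about nil over a change score when the baseline SD is half the Day 28 SD, and about nil for colonization when almost no infant is colonized at baseline.

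The case for adjusting is robustness. Each unadjusted option does badly somewhere in the plausible range, while rank ANCOVA was best or within about 2 points of best in every scenario above. The size for this trial cannot be known from the documents.

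**What to change.** In Section 9.2.3, before the unblinded interim look in Section 9.3:

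1. Name one scalar composition measure as primary, for example total *Bifidobacterium* abundance, which Section 6.3.3.5 already lists. No adjustment can be specified without this step.
2. Compare its Day 28 value between arms with Quade's rank ANCOVA, adjusting for the infant's baseline value of the same measure.
3. Keep the unadjusted Wilcoxon test as a sensitivity analysis, and state whether it ranks the change or the Day 28 value.
4. The *B. infantis* colonization measure may stay unadjusted.

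The cost is the choice of measure, a few lines of text, and the protocol amendment with IRB review that Section 9.4 requires for changes to principal analysis features. No new infants, visits or samples are needed, and the test stays rank-based. The downside is a power loss of up to about 2 points in some scenarios.

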9.2.4 Study Participant Baseline Characteristics and Demographics

Summary of descriptive statistics for baseline and demographic characteristics will be provided for all enrolled participants. Demographic data will include age, race, sex, body weight, and height; these data will be presented in summary tables.

9.2.5 Study Completion

Premature Termination of Study: Should it prove necessary to discontinue the study permanently prior to completion, the Sponsor will notify Infinant Health and the IRB of the rationale. Participants will be informed by the study site. All relevant study documents and data will then be returned to the Sponsor, and the study product will be destroyed or returned.

Termination of Study: After the completion or termination of the study, all relevant study documents and data will then be sent to the Sponsor and the study product will be destroyed. The Investigator will inform the IRB of the end of the study and a certificate of study closure will be issued.

9.3 Interim Analyses

One Interim Analysis will occur when the first 10 subjects (at least) complete the study. Interim Analysis data will be analyzed and reported by an unblinded statistician.

9.4 Deviations from Statistical Plan

The principal features of the study design and of the plan for statistical analysis of the data are outlined in this protocol. Any changes in these principal features will require a protocol amendment and will be described in the final report. Any such changes will be subject to review by the IRB.

9.5 Documenting an Unblinding

Any unblinding will require a full written account of the event(s) that necessitated the unblinding of the treatment assignment for an individual participant(s). This account will be made in the participant(s) study file and in the final study report and will include the reason(s) for the unblinding, the name of the Independent Study Monitor who was notified and approved the unblinding, the names of the individuals unblinded, and the date and time the unblinding occurred.

10 MONITORING AND QUALITY ASSURANCE

10.1 SAFETY PROCEDURES

10.1.1 Stopping Rules

10.1.1.1 Study Stopping Rules

Study enrollment and study procedures will be suspended pending expedited review of all pertinent data by the Partners institutional review board (IRB), the ISM, and the Infinant Medical Officer, if a participant at any time or in any group develops a severe or life-threatening adverse event such that he or she requires hospitalization, or an unexpected (non-allergy-related) hospitalization or death.

Study enrollment will be suspended pending expedited review of all pertinent data by the ISM if any of the following occur:

- Any death related to *B. infantis* INF108F
- Any serious adverse reaction to *B. infantis* INF108F

All above events will be reported immediately to the Partners IRB, the ISM, and Infinant's Medical Officer. The study will not resume until approval is given by the IRB, the ISM, and Infinant's Medical Officer.

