6.4 Study Procedures

All study procedures are listed in **Table 1: Schedule of Events** below.

Table 1: Schedule of Events

	Screening	Day 0 (Baseline)	Days 1-6	Day 7	Days 8-13	Day 14	Days 15-27	Day 28 (End of Study)
Diagnosis	x							
Consent	x							
Screening	x							
Study Visit	x	x		x		x		x
Physical exam		x		x		x		x
Supplementation			x	x	x	x		
Questionnaire		x	x	x	x	x	x	
Feeding log		x	x	x	x	x	x	
Stooling log		x	x	x	x	x	x	
Clinician symptom tool		x		x		x		x
Randomization		x						
Stool collection		x	x	x		x		x
Hemoccult test		x	x	x	x	x	x	x
Stool to site				x				x
AE reporting			x	x	x	x	x	x

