- A life-threatening event. A life-threatening event is any adverse experience that, in the view of the investigator, places the study participant at immediate risk of death from the reaction as it occurred. It does not include an adverse event or suspected adverse reaction that, had it occurred in a more severe form, might have caused death.
- An inpatient hospitalization or prolongation of existing hospitalization.
- Persistent or significant disability/incapacity or substantial disruption of the ability to conduct normal life functions.
- An important medical event that may not result in death, be life threatening, or require hospitalization may be considered an SAE when, based on appropriate medical judgment, it may jeopardize the participant and may require medical or surgical intervention to prevent one of the outcomes listed above.
- Congenital anomaly or birth defect.

Regardless of the relationship of the adverse event to the study, the event will be reported per Section 8.2.2.3 as an SAE if it meets any of the above definitions.

10.2.1.5 Unexpected Adverse Event An AE or SAR (including AR) is considered “unexpected” if it is not consistent with the risk information described in the study protocol.

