There is no risk for possible anaphylaxis with our study agent INF108F and placebo. Epinephrine auto injectors and diphenhydramine will not be needed. Potential gastrointestinal adverse effects might occur, including abdominal discomfort and changes of stool frequency and consistency. We will stop administering the study agent if any of adverse events occur and we will treat the symptoms accordingly.

The same protocol will be recommended when signs/symptoms of acute gastrointestinal infection occur. An adverse event will be followed until any of the following takes place: a) it is resolved, b) participant is stable, c) a minimum of 30 days after participant is terminated from the study and the Independent Safety Monitor and the

Principal Investigator determine that follow-up is complete. If an abnormal value or result is determined by the investigator to be clinically significant, it must be recorded as an adverse event on the appropriate laboratory evaluation form(s).

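### Section 10.1.1.1 gives a serious product reaction without admission or death a narrower stated hold than an unrelated admission, and sets no default for home dosing of other infants

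*Combined protocol and SAP*

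**What the plan says.** The first rule in Section 10.1.1.1 begins "Study enrollment and study procedures will be suspended pending expedited review of all pertinent data by the Partners institutional review board (IRB" and adds the ISM and the company's Medical Officer as reviewers. It is met by an adverse event grave enough to need admission, or by an unexpected, non-allergy admission or death, in any group. It sets no condition that the product be the cause.

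The second rule reads "Study enrollment will be suspended pending expedited review of all pertinent data by the ISM if any of the following occur". Its two triggers are a death related to the product and a serious adverse reaction to it. It names enrollment only.

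A closing sentence covers both rules: "The study will not resume until approval is given by the IRB, the ISM, and Infinant's Medical Officer".

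Other relevant text:
- Section 10.2.1.4, on seriousness: "An important medical event that may not result in death, be life threatening, or require hospitalization may be considered an SAE".
- Section 5.4, on dispensing: "Feeding kits to include 14 sachets of study product". Section 6.1.2 has parents keep the product in the home freezer.
- Section 10.2.2.4, on managing adverse events: "We will stop administering the study agent if any of adverse events occur and we will treat the symptoms accordingly".
- Section 10.2.4.1: the Medical Officer and the ISM are told of any SAE within 24 hours, and they and the investigator discuss its impact within a further 24 hours.
- The synopsis lists the study procedures as "Physical examination, stool collection, questionnaire administration". Section 6.4 says "All study procedures are listed in" Table 1, which has rows for supplementation, stool collection, hemoccult testing and adverse event reporting.

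**The concern.** The reach of the hold does not follow the risk signal. A serious reaction attributed to the product is the event that says most about danger to other infants on it, yet it carries the narrower stated suspension. Stopping enrollment protects infants not yet randomized. It does nothing for families already giving a daily dose at home, because someone has to tell them to stop and the rule does not say so. Appendix A states that there is no separate monitoring committee and points to Section 10 for safety procedures, so this wording carries more weight than it otherwise would.

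The first rule has a smaller, opposite problem. It suspends study procedures without saying which, so staff could take it to include diaper stool collection. Section 7.2.3 says that collection carries no risk, and it supplies the Baseline-to-Day-28 primary endpoint.

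**Working it through.** The plan gives no figure on this point, so the check is mainly of the text.

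**1. Which rule catches which event**

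| Event | First rule | Second rule | Stated hold |
|---|---|---|---|
| Product-related death (taken as unexpected) | met | met | enrollment and procedures |
| Serious product reaction with a severe or unexpected admission | met | met | enrollment and procedures |
| Serious product reaction, no admission or death | not met | met | enrollment only |
| Unexpected non-allergy admission, unrelated to product | met | not met | enrollment and procedures |

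The gap is confined to the third row. Section 10.2.1.4 makes that row possible.

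**2. Does other text order a hold in other infants?**
- Section 10.1.1.2 withdraws the participant who has the event.
- Section 10.2.2.4 speaks of stopping the agent and treating the symptoms, which reads as care of the affected infant.
- Section 10.2.4.1 sets up a discussion of the effect on the study, but no hold while it is awaited.
- The restart sentence implies a pause of the whole study, but does not say that dosing is part of it.

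The first rule does not name dosing either. Table 1 counts supplementation among the procedures, while the synopsis list does not.

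**3. How long the default matters**

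24 hours to notify + 24 hours to discuss = 48 hours from the site becoming aware. This assumes that the discussion settles dosing. At one dose a day, that is about 2 doses per infant on product.

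**4. How many other infants (illustration)**

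From the plan: 50 randomized and 14 days of product. Assumed, because no accrual period is given: even accrual over M months. Drop-out is ignored.

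Rate r = 50 / (365 × M/12) per day; infants on product = 14r.
- M = 6: r = 0.274, 14r = 3.8
- M = 12: r = 0.137, 14r = 1.9
- M = 24: r = 0.068, 14r = 1.0

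Over 48 hours this is about 2 × 1.0 = 2 to 2 × 3.8 = 7.6 doses in all. With 1:1 allocation, about half of them are active.

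**5. Does suspending procedures stop stool collection?**

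Stool collection is in both lists of procedures. But adverse event reporting is also a row of Table 1, and Section 10.2.2.1 plainly requires it to continue. The phrase therefore need not cover every row. The text leaves stool collection open.

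**The case against.** The strongest case is that the section works as a whole. Both rules require immediate reporting, and a study that needs three approvals to resume has been paused. Section 10.2.4.1 gives a named, time-limited forum for deciding about other infants. The triggering event should be rare: Section 7.1 reports no known side effects, and the GRAS level in Section 1.5.1 (2.8 × 10^10 CFU/day) is 3.5 times the study dose (8.0 × 10^9). Halting all procedures until review is also a legitimate cautious choice. This limits the size and likelihood of the problem. It does not supply the missing default, and staff should not have to infer one from a restart clause.

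Two stronger readings are tempting.

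A reader might infer that the second rule means dosing of other infants is to carry on. The documents do not support this, because the restart sentence points the other way. The text is ambiguous.

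A reader might also infer a countable loss of primary-endpoint samples. A suspension covers the whole Day 28 window (days 27–29) for starts on 5 of 28 study days if it lasts an assumed 7 days, on 12 of 28 if 14 days, and on none if 2 days or less. Multiplying by r gives 5 × 0.0685 = 0.3 (24-month accrual, 7 days) to 12 × 0.274 = 3.3 (6-month accrual, 14 days) covered windows per suspension. These are covered windows, not lost samples. Section 6.3.3.1 asks only for best efforts on timing, and no section discards a late sample. Families hold stool kits. Section 6.3.2.1 also schedules a Day 21 stool, which in the 7-day case would already be due. Accrual, suspension length and the suspension itself are all assumed.

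**Conclusion.** The point holds as a cheap wording improvement. A serious product reaction without admission or death has a narrower stated hold than an unrelated unexpected admission, and no text sets a default for home dosing of other infants. The ambiguity lasts about 48 hours if the discussion in Section 10.2.4.1 resolves it, and would touch about 1 to 4 infants under the assumed accrual periods. The plan gives no event rate, so how often this would arise is unknown.

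The stool point is only a clarification. Day 28 samples could be late or missing, and Section 9.2.2 rules out imputation, but no number of lost primary-endpoint samples is established. Adverse event recording and follow-up are secured elsewhere (Sections 10.1.3 and 10.2.2). Nothing here affects the sample size or the analysis.

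**What to change.** Amend Section 10.1.1.1 in three places:
1. In both rules, suspend enrollment and study product administration.
2. Have the site tell all families with product at home to stop using their sachets until the review is complete.
3. State that adverse event follow-up, diaper stool collection, hemoccult cards and parent logs continue in randomized infants during a suspension.

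The cost is one IRB-reviewed amendment, with no added participants, visits or staff. The downside is that a blinded halt can follow a placebo event and may interrupt the 14-day course of the few infants then on product, in either arm. Those who have had at least one dose stay in the mITT population. Whether a held course is a major deviation can be settled in the definitions that Section 9.2.2 already requires before unblinding.
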